### 6.2.2 Prohibited medication

Use of the treatments displayed in [Table 6-3](#) are NOT allowed after the start of study treatment until the patient's final dose of oral study medication (nidufexor or placebo).

Nidufexor is metabolized primarily by UGT1A1. There is a potential for inhibitors of UGT1A1 to affect the clearance of nidufexor. There is also a potential that nidufexor will affect the disposition of medications that are substrates of CYP2C8.

**Patients with known Gilbert’s syndrome and those taking concomitant medications and herbal remedies that inhibit UGT1A1 or are a profound CYP2C8 substrate should be EXCLUDED from clinical trials of nidufexor until formal clinical drug-drug interaction studies have been performed.**

**Restricted Antihyperglycemic Medications:** The SGLT-2 inhibitors (e.g. canagliflozin, dapagliflozin, empagliflozin) and GLP-1 receptor agonists (e.g. exenatide, liraglutide, albiglutide, dulaglutide, semaglutide, lixisenatide) are prohibited medications in this study. A list of generic and trade names is provided in the SOM.

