  - Total Bilirubin >120% X ULN or Gilbert's syndrome
  - Alkaline phosphatase >300U/L
  - History of esophageal varices, ascites or hepatic encephalopathy
  - Splenomegaly
  - Platelet count <LLN

Commercially Confidential Information

18. Receiving any of the prohibited medications listed in [Table 6-2](#), (e.g. UGT1A1 inhibitors, herbal remedies that inhibit UGT1A1, non-selective UGT inhibitors, ACEI and ARB in combination, direct renin inhibitors, SGLT2 inhibitors, GLP1-receptor agonists) and unable to switch to suitable alternatives at least 5 days prior to first study dose and for the duration of the study
19. History of non-adherence to medical regimens, or patients who are considered by the investigator to be unable to reliably comply with the requirements of the study.
20. History of treated or untreated malignancy of any organ system, other than localized basal cell carcinoma of the skin or treated cervical intraepithelial neoplasia, within the past 5 years of screening, regardless of whether there is evidence of local recurrence or metastases
21. History or current diagnosis of ECG abnormalities prior to first study dose indicating significant risk of safety for patients participating in the study
22. Donation or loss of >400 mL or more of blood within eight (8) weeks prior to initial dosing, or longer if required by local regulation
23. Known positivity for Human Immunodeficiency Virus (HIV) infection
24. Women of childbearing potential, defined as all women physiologically capable of becoming pregnant, **unless** they are using basic methods of contraception during dosing of study treatment.

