## 6.2 Other treatment(s)

### 6.2.1 Concomitant therapy

Treatment other than study treatment is permitted through the entire study duration, if such treatment is not prohibited as defined in [Section 6.2.2](#).

Hormonal contraception is allowed during this study (see [Section 5.2](#)).

All medications, procedures and significant non-drug therapies (including physical therapy and blood transfusions) administered after the patient was enrolled into the study must be recorded in the concomitant medications / significant non-drug therapies or procedures pages.

Each concomitant drug must be individually assessed against all exclusion criteria/prohibited medication.

If in doubt the investigator should contact the Novartis translational medical expert, or designee, before randomizing a patient or allowing a new medication to be started. If the patient is already enrolled, the investigator should contact the Novartis translational medical expert, or designee, to determine if the patient should continue participation in the study.

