#### 6.2.1.1 Permitted concomitant therapy requiring caution and/or action

*Persistent Hyperglycemia:* Investigators are advised to manage glycemic control for all patients in a manner consistent with local treatment guidelines for type 2 diabetes. In the absence of local guidelines, investigators are referred to the joint ADA/EASD guidelines for the management of glucose control in patients with type 2 diabetes ([Inzucchi et al 2015](#)).

*Dose Adjustments:* Nidufexor may moderately reduce the clearance of medications that are substrates of CYP2C8. Administration of nidufexor with pioglitazone, rosiglitazone, or glyburide (glibenclamide) could result in higher serum concentrations of these medications, thereby increasing the potential for hypoglycemia. Frequent, regular fingerstick blood glucose monitoring is advisable during the treatment phase of this study, with subsequent dose adjustments of these medications as needed.

*NSAIDs, COX-2s:* Modest doses of non-steroidal anti-inflammatory drugs (NSAIDs) or selective cyclooxygenase-2 (COX-2) inhibitors may be used for a period not longer than 7 days.

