**Table 6-2 Prohibited medication**

Medication	Prohibition period	Action taken
Specific UGT1A1 inhibitors: e.g atazanavir, gemfibrozil, indinavir, itraconazole, ketoconazole, manidpine, and zafirlukast	Any use from first drug intake to end-of-study visit	Discontinue UGT1A1 inhibitor, if possible. Stop nidufexor. Check a random nidufexor level, noting time elapsed since last dose.
Herbal remedies inhibiting UGT1A1:e.g Silybum marianum (sylamarin, milk thistle) and Valeriana officinalis (valerian)	Any use from first drug intake to end-of-study visit	Discontinue herbal remedy. Stop nidufexor and check a random nidufexor level, noting time elapsed since last dose.
Non-selective UGT inhibitors: e.g diclofenac, probenecid, valproic acid	Any use from first drug intake to end-of-study visit	Discontinue non-selective UGT inhibitors, if possible. Stop nidufexor and check a random nidufexor level, noting time elapsed since last dose.
Aliskiren, direct renin inhibitors	Any use from first drug intake to end-of-study visit	Discontinue direct renin inhibitor, if possible. If not possible, stop nidufexor and check a random nidufexor level, noting time elapsed since last dose.
ACEI + ARB in combination	Any use from first drug intake to end-of-study visit	Discontinue either ARB or ACE inhibitor, if possible. If not possible, stop nidufexor and check a random nidufexor level, noting time elapsed since last dose
Sodium-glucose co-transporter 2 (SGLT2) inhibitors	Any use from first drug intake to end-of-study visit	Discontinue SGLT2 inhibitors, if possible. If not possible, stop nidufexor and check a random nidufexor level, noting time elapsed since last dose.
GLP-1 receptor agonists	Any use from first drug intake to end-of-study visit	Discontinue GLP-1 receptor agonists, if possible. If not possible, stop nidufexor and check a random nidufexor level, noting time elapsed since last dose.

Patients on medications specified in [Table 6-3](#) can be included if the investigator determines the following criteria have been met:

- Usage is considered medically necessary, and
- Dose has been stable for at least 1 month prior to screening, and
- Dose is expected to remain stable for the duration of the study

No new use of these medications is allowed after entering the study, with the exception of drugs to control medically significant elevations in LDL-C, which has been confirmed upon repeat testing.

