A stable dose of insulin is defined as being within 25% of the current dose. A stable dose of oral anti-diabetic medications is defined as up to one step-up or step-down from the dose at randomization, per local treatment guidelines. For all other medications listed in [Table 6-3](#), the definition of stable will be left to investigator discretion.

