**Table 6-3 Permitted medication if dose is stable for at least 1 month prior to randomization**

Medication

• Oral anti-diabetic medications such as metformin, sulfonylureas (including glyburide (glibenclamide), meglitinides (such as repaglinide) and thiazolidinediones (including pioglitazone and rosiglitazone)

• Insulin (within 25% of the dose at randomization)

• Beta-blockers and thiazide diuretics. Thiazide diuretic use should also be maintained constant throughout the trial, if possible.

• Fibrates, statins niacin, ezetimibe

• Vitamin E

• Thyroid hormone

• Psychotropic medications (phenothiazines or second generation antipsychotics)

• Hormonal (estrogen, progesterone, or estrogen/progesterone containing) birth control

There is a potential for nidufexor to increase exposure of drugs metabolized by CYP2C8 (including repaglinide, pioglitazone and rosiglitazone) and those dependent on export by BCRP (potentially glyburide (glibenclamide), atorvastatin, rosuvastatin and pitavastatin). Careful attention MUST be paid to the drug interaction sections of the prescribing information for these compounds

Unless adjustment is required due to intercurrent illness;

Unless adjustment is required to treat medically significant increases in LDL-C that have been confirmed upon repeat testing.

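### Protocol 6.2.2 opens by banning the permitted-drug table instead of the prohibited one, and the NSAID and fibrate permissions do not except diclofenac and gemfibrozil, which Table 6-2 prohibits

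*Protocol*

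**What the plan says.** Section 6.2.1 allows treatment other than study treatment unless 6.2.2 prohibits it. Section 6.2.2 opens with: "Use of the treatments displayed in [Table 6-3](#) are NOT allowed after the start of study treatment". The ban in that sentence runs to the final dose of study medication.

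Table 6-3 is titled "Permitted medication if dose is stable for at least 1 month prior to randomization". Two later statements in 6.2.2 treat it that way: "Patients on medications specified in [Table 6-3](#) can be included if the investigator determines the following criteria have been met", and "For all other medications listed in [Table 6-3](#), the definition of stable will be left to investigator discretion". Section 6.2.1 adds: "Hormonal contraception is allowed during this study". The last line of Table 6-3 is "Hormonal (estrogen, progesterone, or estrogen/progesterone containing) birth control".

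Table 6-2 is the table titled as prohibited medication. Exclusion criterion 18 in section 5.2 points to it: "Receiving any of the prohibited medications listed in [Table 6-2".

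On classes of drug, section 6.2.1.1 says that modest doses of NSAIDs or COX-2 inhibitors "may be used for a period not longer than 7 days", and Table 6-3 lists fibrates. Table 6-2 names gemfibrozil among the specific UGT1A1 inhibitors and diclofenac among the non-selective UGT inhibitors. Both are barred from first dose to the end-of-study visit.

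**The concern.** There are two separate defects.

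First, the sentence that introduces the prohibited medications names the wrong table. It bans background drugs that patients with type 2 diabetes will commonly be taking and that the protocol elsewhere lets them keep. It also fails to point to the list that matters. Because 6.2.1 refers to 6.2.2 for the definition of prohibited treatment, the error sits in the definition.

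Second, two class-wide permissions include a drug that Table 6-2 prohibits by name, and neither makes an exception. A patient given a short course of diclofenac under the NSAID permission would meet the Table 6-2 instruction to stop nidufexor and check a level. That is an avoidable treatment stop and protocol deviation for that patient. The underlying reason concerns safety: 6.2.2 says nidufexor is cleared mainly through UGT1A1 and that inhibitors may alter its clearance.

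**Working it through.** No arithmetic applies beyond counting. The check sets the passages side by side.

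**Wrong table**

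| Place in protocol | Table cited | How the table is treated |
|---|---|---|
| 6.2.2, opening sentence | 6-3 | prohibited |
| 6.2.2, text after Table 6-2 | 6-3 | permitted under conditions |
| 6.2.2, stable-dose definition | 6-3 | permitted if stable |
| Table 6-3, title | 6-3 | permitted if stable |
| 5.2, exclusion criterion 18 | 6-2 | prohibited |
| Table 6-2, title | 6-2 | prohibited |

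- The text of 6.2.2 refers to Table 6-3 three times. One reference (the opening sentence) treats it as prohibited and two treat it as permitted.
- Table 6-3 has 8 lines: oral anti-diabetics; insulin; beta-blockers and thiazides; fibrates, statins, niacin and ezetimibe; vitamin E; thyroid hormone; psychotropics; hormonal birth control. The literal sentence bans all 8.
- Table 6-2 has 7 rows. The opening sentence refers to none of them.
- Hormonal birth control shows the conflict most plainly: 6.2.1 allows it, and the literal sentence forbids it.
- Replacing 6-3 with 6-2 in the opening sentence makes all six rows above agree.

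**Overlapping permissions**

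That diclofenac is an NSAID and gemfibrozil a fibrate is general pharmacology; the documents do not state it.

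| Drug | Class permission | Exception stated? | Table 6-2 row | Action for nidufexor |
|---|---|---|---|---|
| Diclofenac | 6.2.1.1, NSAIDs, at most 7 days | none | non-selective UGT inhibitors | stop, check level |
| Gemfibrozil | Table 6-3, fibrates | none | specific UGT1A1 inhibitors | stop, check level |

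The action is stricter here than for most of the table. In 4 of the 7 rows (direct renin inhibitors, ACEI plus ARB, SGLT2 inhibitors, GLP-1 agonists) nidufexor is stopped only if the other drug cannot be. In the other 3 rows (specific UGT1A1 inhibitors, herbal remedies, non-selective UGT inhibitors) the stop carries no such condition. Diclofenac and gemfibrozil both fall in those 3.

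The two defects do not compound for gemfibrozil. As a fibrate it falls within Table 6-3, so the misdirected opening sentence errs toward prohibiting it.

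**The case against.** The best case for leaving this alone is that the intended meaning is easy to recover and the ban already prevails.

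- The section heading, the title of Table 6-2, and its own columns for prohibition period and action impose the ban without help from the opening sentence. The body of 6.2.2 also names UGT1A1 inhibitors, SGLT2 inhibitors and GLP-1 agonists as excluded or prohibited.
- Section 6.2.1 makes every permission subject to 6.2.2, requires each drug to be checked individually, and sends doubtful cases to the sponsor's medical expert.
- Section 6.2.2 bars new use of Table 6-3 drugs after entry, apart from drugs for confirmed LDL-C elevation. The literal contradiction therefore bears on continued stable use, which the later text of 6.2.2 addresses directly. It is hard to imagine a site stopping insulin because of this sentence.
- For gemfibrozil, exclusion criterion 18 catches use at entry and the bar on new use limits it afterwards.

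All of this is correct and keeps the point minor. It does not remove it. The protocol still states conflicting rules on a drug interaction for which it requires treatment to stop. The diclofenac case arises on study, where a site may look only at the NSAID permission. A safeguard that depends on the investigator noticing a contradiction is a weak reason to leave the contradiction in place.

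**Conclusion.** The point holds as a minor safety correction that should be made. One of the three references to Table 6-3 in 6.2.2 is wrong; taken literally it bans 8 permitted lines and does not point to the 7 prohibited rows. Separately, two drugs prohibited by name fall under two class permissions that make no exception for them. The prohibition prevails under 6.2.1 and exclusion criterion 18, which should normally prevent harm. The documents give no usage figures, so how often a site would be misled cannot be estimated. No effect on the analysis is claimed. The only outside assumption is the drug class of diclofenac and gemfibrozil.

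**What to change.** Three edits to the protocol, and a notice to sites:

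1. In the first sentence of 6.2.2, replace Table 6-3 with Table 6-2. In the same edit it would be tidy to align the end of the ban. The sentence stops at the final dose, whereas Table 6-2 runs to the end-of-study visit, a difference of one day for completers (Day 168 against Day 169).
2. In Table 6-3, write fibrates (except gemfibrozil).
3. In the NSAID line of 6.2.1.1, add an exception for diclofenac and other UGT inhibitors, with a pointer to Table 6-2.

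The cost is a few words in three places and the site notification. Design, data collection and analysis do not change, and no clinical decision is reopened, because the prohibition already prevails.

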**Table 6-2 Prohibited medication**

Medication	Prohibition period	Action taken
Specific UGT1A1 inhibitors: e.g atazanavir, gemfibrozil, indinavir, itraconazole, ketoconazole, manidpine, and zafirlukast	Any use from first drug intake to end-of-study visit	Discontinue UGT1A1 inhibitor, if possible. Stop nidufexor. Check a random nidufexor level, noting time elapsed since last dose.
Herbal remedies inhibiting UGT1A1:e.g Silybum marianum (sylamarin, milk thistle) and Valeriana officinalis (valerian)	Any use from first drug intake to end-of-study visit	Discontinue herbal remedy. Stop nidufexor and check a random nidufexor level, noting time elapsed since last dose.
Non-selective UGT inhibitors: e.g diclofenac, probenecid, valproic acid	Any use from first drug intake to end-of-study visit	Discontinue non-selective UGT inhibitors, if possible. Stop nidufexor and check a random nidufexor level, noting time elapsed since last dose.
Aliskiren, direct renin inhibitors	Any use from first drug intake to end-of-study visit	Discontinue direct renin inhibitor, if possible. If not possible, stop nidufexor and check a random nidufexor level, noting time elapsed since last dose.
ACEI + ARB in combination	Any use from first drug intake to end-of-study visit	Discontinue either ARB or ACE inhibitor, if possible. If not possible, stop nidufexor and check a random nidufexor level, noting time elapsed since last dose
Sodium-glucose co-transporter 2 (SGLT2) inhibitors	Any use from first drug intake to end-of-study visit	Discontinue SGLT2 inhibitors, if possible. If not possible, stop nidufexor and check a random nidufexor level, noting time elapsed since last dose.
GLP-1 receptor agonists	Any use from first drug intake to end-of-study visit	Discontinue GLP-1 receptor agonists, if possible. If not possible, stop nidufexor and check a random nidufexor level, noting time elapsed since last dose.

Patients on medications specified in [Table 6-3](#) can be included if the investigator determines the following criteria have been met:

- Usage is considered medically necessary, and
- Dose has been stable for at least 1 month prior to screening, and
- Dose is expected to remain stable for the duration of the study

No new use of these medications is allowed after entering the study, with the exception of drugs to control medically significant elevations in LDL-C, which has been confirmed upon repeat testing.

A stable dose of insulin is defined as being within 25% of the current dose. A stable dose of oral anti-diabetic medications is defined as up to one step-up or step-down from the dose at randomization, per local treatment guidelines. For all other medications listed in [Table 6-3](#), the definition of stable will be left to investigator discretion.

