In addition, investigators will be advised to manage glycemic control for all patients in a manner consistent with local treatment guidelines for type 2 diabetes. In the absence of local guidelines, investigators are referred to the joint ADA/EASD guidelines for the management of glucose control in patients with type 2 diabetes ([Inzucchi et al 2015](#)).

The assessment of the Benefit/Risk for the study in the context of COVID-19 pandemic concluded the absence of additional risks for the study population and/or related to the investigational medicinal product.

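### Protocol 6.2.2 bars starting insulin or any oral anti-diabetic when glycemic control worsens, although 4.5 and 6.2.1.1 advise guideline-based care for all patients

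*Protocol*

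**What the plan says.** **The advice.** Protocol Section 4.5 states that "investigators will be advised to manage glycemic control for all patients in a manner consistent with local treatment guidelines for type 2 diabetes". Section 6.2.1.1 repeats this in its entry on persistent hyperglycemia, and the title of that section describes permitted therapy: "Investigators are advised to manage glycemic control for all patients in a manner consistent with local treatment guidelines for type 2 diabetes".

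**The restriction.** Section 6.2.1 allows other treatment only where it is "permitted through the entire study duration, if such treatment is not prohibited as defined in" Section 6.2.2. Section 6.2.2 admits patients who already take Table 6-3 drugs at a stable dose that is expected to stay stable. It then says: "No new use of these medications is allowed after entering the study, with the exception of drugs to control medically significant elevations in LDL-C". Table 6-3 lists insulin and an open-ended group of oral anti-diabetics. SGLT2 inhibitors and GLP-1 receptor agonists "are prohibited medications in this study".

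**The room for titration.** Section 6.2.2 counts an oral agent as stable if it moves by no more than one step from the randomization dose, and insulin if it stays within 25%. Footnote 2 of Table 6-3 relaxes the insulin limit for intercurrent illness only.

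**The opening sentence of 6.2.2.** It says that the treatments in Table 6-3 "are NOT allowed after the start of study treatment". Table 6-3 is the list of permitted drugs.

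**The concern.** Guideline care for type 2 diabetes may call for adding a drug when control is lost. The protocol advises such care for everyone, and Section 6.2.2, read as written, then closes every glucose-lowering class it names to new starts. It provides an exception for LDL-C and none for glucose.

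The need is foreseeable. HbA1c up to 11% is allowed at entry, and treatment lasts 24 weeks. Exclusion criterion 18 lets in patients who come off an SGLT2 inhibitor or GLP-1 receptor agonist as little as 5 days before the first dose.

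At stake are the safety of a patient whose control worsens and whether sites handle such patients in the same way. One site may start insulin and record a deviation, another may ask the sponsor, and a third may stop study drug.

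**Working it through.** The plan attaches no figure to this rule, so the check compares the texts, with two small sums.

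**1. Which text governs.** Section 6.2.1 makes permission conditional on 6.2.2. The persistent-hyperglycemia entry in 6.2.1.1 names no drug and states no exception to 6.2.2. The as-needed dose adjustments in 6.2.1.1 concern pioglitazone, rosiglitazone and glyburide already being taken, because nidufexor "could result in higher serum concentrations of these medications, thereby increasing the potential for hypoglycemia". That passage guards against low glucose and does not authorize an add-on for high glucose.

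**2. What is closed to a new start.**
- By the bar on new use of Table 6-3 drugs: metformin, sulfonylureas, meglitinides, thiazolidinediones, any other oral anti-diabetic, and insulin.
- By Table 6-2: SGLT2 inhibitors and GLP-1 receptor agonists.
- Opened by the exception: LDL-C drugs only.

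**3. What titration leaves.** One oral step is allowed. For insulin the reference dose is ambiguous. Table 6-3 uses the randomization dose, which caps the total at 1.25 times that dose. The text above the table uses the current dose, and two successive increases would then give 1.25 × 1.25 = 1.56 times. For a patient on oral agents only, the ambiguity is irrelevant: starting insulin is new use on either reading.

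**4. Routes beyond those limits.**
- Section 6.2.1: consult the sponsor's medical expert. No criterion is given, and for an enrolled patient the stated purpose is "to determine if the patient should continue participation in the study".
- Section 14.1: act for safety and accept a deviation, then notify the sponsor and inform the ethics committee. The clause is worded for immediate action, so it fits acute hyperglycemia better than slow loss of control.
- Section 9.1.1: stop study drug if continuing would harm the patient.

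**5. Does an add-on cost data?** The mandatory discontinuation list in Section 9.1.1 does not name it. The instructions to stop nidufexor in Table 6-2 apply to that table's own rows. In SAP Section 4.1, the only visible exclusion for a concomitant drug is SGLT2 use. So new insulin or metformin triggers neither stopping nor exclusion in the visible text.

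**6. If stopping is chosen anyway.** Section 9.1.1 asks for the final-visit assessments as soon as possible. SAP Sections 2.2 and 4.1 exclude Week 24 assessments done on Day 134 or earlier, which covers 134/168 = 79.8% of the treatment period. Earlier UACR values still enter the MMRM. The 24-hour albumin is taken only at baseline and end of study, so the patient would drop out of its primary ANCOVA. The supplementary ITT analysis in SAP Section 2.5.4 would keep the value.

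**The case against.** The strongest reply has four parts.

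- **The heading.** Section 6.2.1.1 is titled as permitted therapy, and a specific entry on hyperglycemia can be read as permission despite the general sentence in 6.2.1. That reading is tenable. It shows that two sites could reach opposite conclusions, which is itself a reason to settle the wording.
- **Design choice.** Stable background therapy protects the HbA1c comparison. The LDL-C exception has its own reason, since Section 4.5 reports LDL-C elevations with a bile-acid-derived FXR agonist. The lack of a parallel glucose exception is therefore not an error in itself. This stands, but it does not reconcile the restriction with the advice given twice elsewhere.
- **Care is not blocked.** Titration, sponsor consultation and the safety clause all remain. This stands, and it limits the seriousness of the point.
- **The table reference.** The reference to Table 6-3 in the opening sentence of 6.2.2 is probably a slip for Table 6-2. It adds no weight to the point and matters only for the repair.

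A reader might infer that a patient who needs an add-on must leave study drug and so loses the Week 24 values. The documents do not support that. Stopping is one option among three, and no visible rule removes data because insulin or an oral agent was started. Other exclusions may be redacted, so this conclusion is limited to the visible text.

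**Conclusion.** The conflict between the advice and the restriction is real and should be corrected. Beyond one oral step and insulin within 25%, a patient whose control worsens has no add-on that a written rule plainly permits. The gap is clearest for patients on oral agents only.

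The consequence is for patient safety and uniform conduct. The number of patients affected cannot be derived from the documents, so no size can be put on it. The effect on the albuminuria analysis is probably small, because data are lost only if a site chooses to stop study drug. It would be wrong to infer from this point that the primary analysis is compromised.

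The conclusion assumes that Section 6.2.1 makes 6.2.2 the controlling list and that no redacted text supplies a glycemic rescue rule.

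**What to change.** 1. In Section 6.2.2, extend the LDL-C exception to cover insulin, or an oral anti-diabetic that is not in Table 6-2 and is not pioglitazone, rosiglitazone, repaglinide or glyburide, started or increased for persistent hyperglycemia confirmed on repeat testing. Put the same words in footnote 2 of Table 6-3 (insulin) and in a new footnote on the oral anti-diabetic row. The sponsor's clinicians should set the glycemic threshold.
2. In the opening sentence of 6.2.2, change the reference from Table 6-3 to Table 6-2. Otherwise the section would still literally bar the drugs that the first change allows.

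The SGLT2 and GLP-1 prohibitions and footnote 1 of Table 6-3 stay as they are.

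The cost is one sentence, two footnotes and one table reference in an amendment. Background glucose-lowering therapy becomes slightly more variable, which may blur the HbA1c comparison. New starts should be recorded, as Section 6.2.1 already requires, and considered when HbA1c is interpreted. Added insulin or a sulfonylurea carries some hypoglycemia risk. Section 6.2.1.1 already advises regular fingerstick monitoring, and the four agents whose exposure nidufexor may raise remain closed to new starts.
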